1.4 Required power for primary endpoint and noninferiority margin (if applicable)

The sample size calculation was based on both HbA1c and body weight endpoints. The assumed standard deviation for HbA1c and the coefficient of variance for body weight were 1.2% and 3%, respectively. The combined power (calculated as the product of the marginal powers for HbA1c and body weight) was at least 85%. Noninferiority of glycemic control with liraglutide versus glimepiride was concluded if the upper limit of the two-sided 95% CI for the treatment difference was < 0.4%.

With a standard deviation of 1.2% for HbA1c and a coefficient of variance of 3% for body weight, it was concluded that at least 168 subjects were required to complete the treatment in the liraglutide and in the glimepiride, respectively. Assuming a dropout rate of 25% after 26 weeks of treatment, the number of subjects to be randomized was calculated to be 228 in each of the liraglutide and glimepiride treatment groups.

1.5 Secondary endpoint for replication (assay sensitivity) and RCT finding n/a

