1.6 Trial estimate

The HbA1c mean decreases of 1.0% (\pm 0.1) for both the 1.2 and 1.8 mg/day liraglutide groups and 1.0% (\pm 0.1) for glimepiride group. Treatment difference in HbA1c was 0.0% [95% CI: -0.2 to 0.2] for both comparisons liraglutide 1.2 mg/day versus glimepiride and liraglutide 1.8 mg/day versus glimepiride (Nauck M et al. 2009).

2. Person responsible for implementation of replication in Aetion

[name], MPH, implemented the study design in the Aetion Evidence Platform and SAS 9.4. She is not responsible for the validity of the design and analytic choices. All implementation steps are recorded, and the implementation history is archived in the platform.

[figure not shown]
3. Data Source(s)

Optum CDM

4. Study Design Diagram

The study design diagram visualizes key aspects of the longitudinal study design for expedited review.

Figure 1. Design Diagram - LEAD-2 TRIAL REPLICATION

5. Cohort Identification

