6.3.1 Outcome variables

Effectiveness outcome variables of interest (definitions provided in **Appendix A**):

• **Primary outcome:** Changes in HbA1c from baseline to 26 weeks of treatment (end of follow-up).

Note. In the trial, HbA1c was also measured at 8, 12, 18 weeks (± 3 days) after randomization. Missing values of HbA1c at 26 weeks were replaced using last observation carried forward (LOCF) in the intention-to-treat (ITT) analysis set. In the replication, HbA1c at baseline will be defined as the last recorded HbA1c value measured within 90 days before and including cohort entry date in both groups. HbA1c at the end of follow-up will be defined as a recorded HbA1c value closest to the end of the 26th week and measured between 56 and 212 days (8-30 weeks) after cohort entry.

Secondary outcome: --

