6.3.2 Primary analysis and study follow-up

As-treated (AT) analysis will be performed as main analysis. The treatment drug will be defined as the index drug assigned on the day of cohort entry. Patients will be followed for about 30 weeks (212 days). Compared to the trial (Nauck M et al. 2009), we will

extend the follow-up and the outcome assessment periods of 4 weeks. The follow-up and outcome assessment window will start 56 days after cohort entry date and will continue until the earliest date of the following events:

- The first occurrence of the outcome of interest (measured between 56 and 212 days after cohort entry),
- The date of end of continuous registration in the database (disenrollment or end of available data),
- End of the study period,
- Measured death event occurs,
- Index drugs discontinuation (liraglutide, glimepiride or metformin),
- Crossover or addition of drug from the other treatment group,
- Addition of any other anti-diabetic medications,
- Nursing home admission
 - Nursing home admissions are considered a censoring event because the data sources utilized typically provide little to no data on a patient, particularly on drug utilization, after admission. We will utilize this as an exclusion reason for cohorts for the same reason.

Note. To decrease the incidence of missing values of the outcome (specifically, missing of HbA1c values measured between 56-212 days after cohort entry), we required that the eligible patients had at least 3 HbA1c measurements recorded within 365 days before and including cohort entry. This will increase the probability of including in the final cohort patients who are adherent to a routinely HbA1c testing and, consequently, will decrease the frequency of missing values of the outcome. Multiple imputation will be used to handle missing values in the primary analysis, while complete case analysis will be applied in a sensitivity analysis.

7. Initial Feasibility Analysis

Aetion report name:

For liraglutide vs. glimepiride

Optum CDM (continuous HbA1c outcome) https://bwh-dope.aetion.com/projects/details/1688/rwrs/71723

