Optum CDM (binary HbA1c outcome [flag: presence or absence of an HbA1c result within 56-212 days after cohort entry]) – calculated merging the databases from $\frac{https://bwh-dope.aetion.com/projects/details/1688/rwrs/71715}{https://bwh-dope.aetion.com/projects/details/1688/rwrs/71715}$ and $\frac{https://bwh-dope.aetion.com/projects/details/1688/rwrs/71715}{https://bwh-dope.aetion.com/projects/details/1688/rwrs/71715}$

dope.aetion.com/projects/details/1688/rwrs/71716 – see file LEAD-2_programming_steps and output of "STEP 1 - Initial FEASIBILITY Analysis (with study outcome) - Paragraph 7 of the protocol"

Date conducted: 06/17/2021

Complete Aetion feasibility analysis using age and CCI as the only covariates and the primary endpoint (Section 6.3.1) as the outcome. No measures of association will be computed nor will mean and standard deviation of the HbA1c outcome stratified by treatment group.

• Report patient characteristics by treatment group For liraglutide vs. glimepiride

	Optum CDM		
	Glimepiride - Comparator	Liraglutide - Exposure	Difference
Number of patients *	3,096	378	- (-, -)
Age			
mean (sd)	64.24 (10.37)	59.22 (10.94)	5.02 (3.90, 6.13)
median [IQR]	67.00 [58.00, 72.00]	60.00 [51.00, 68.00]	- (-, -)
Gender			
M = MALE; n (%)	1,726 (55.7%)	179 (47.4%)	8.39% (3.08%, 13.7%)
F = FEMALE; n (%)	1,370 (44.3%)	199 (52.6%)	-8.39% (-13.7%, -3.08%)
Combined Comorbidity Score - CCI (180 days)			
mean (sd)	2.06 (1.56)	1.86 (1.36)	0.19 (0.03, 0.36)
median [IQR]	2.00 [1.00, 3.00]	2.00 [1.00, 2.00]	- (-, -)

^{*} The overall n. of patients in the unmatched cohort is 3,470. Patients who were censored between cohort entry and the beginning of the outcome assessment window (n. 290 patients) are excluded from the Table reporting patient characteristics by groups because they will not contribute to the unmatched or matched cohorts.

• Report summary parameters of study population **FEASIBILITY- FOR STUDY OUTCOME For** liraglutide vs. glimepiride

	Optum CDM
Number of patients in full cohort	3,764
Number of patients that did not begin follow-up *	290
Number of patients	3,474
Number of person-years of patients that did begin the follow-up	1,118.53
Number of patients in group: Glimepiride	3,096
Number of patients in group: Liraglutide	378
Outcome - Lab value HbA1c	
mean (sd)	7.24 (1.01)
median [IQR]	7.00 [6.60, 7.70]
minimum	4.1
maximum	13.4
Number of patients with zero value	0
Non-zero mean value (SD)	7.24 (1.01)

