Non-zero median value [IQR]	7.00 [6.60, 7.70]

^{*} patients who were censored between cohort entry and the beginning of the outcome assessment window/follow-up (i.e., 0.5-56 days after cohort entry) will not contribute to the unmatched and matched cohorts.

• Report median follow-up time by treatment group For liraglutide vs. glimepiride

Median Follow-Up Time (Days) [IQR] – AT analysis		
Patient Group Optum CDM		
Overall Patient Population	99 [84, 148]	
Referent	101 [84, 148]	
Exposure	88 [79, 130]	

• Report reasons for censoring in the overall study population

• For liraglutide vs. glimepiride

	Overall (n. 3,470)	Liraglutide (n. 378)	Glimepiride (n. 3,092)
Outcome *	2,262 (65.2%)	233 (61.6%)	2,029 (65.6%)
Death	2 (0.1%)	0 (0%)	2 (0.1%)
Start of an additional exposure	8 (0.2%)	3 (0.8%)	5 (0.2%)
End of index exposure	368 (10.6%)	74 (19.6%)	294 (9.5%)
Maximum follow-up time	336 (9.7%)	22 (5.8%)	314 (10.2%)
End of patient data	37 (1.0%)	3 (0.8%)	34 (1.1%)
End of patient enrollment	108 (3.1%)	12 (3.2%)	96 (3.1%)
Start of additional antidiabetic drugs + Nursing home + Metformin discontinuation with allowed 60 days gap	349 (10.1%)	22 (5.82%)	314 (10.2%)

^{*} patients with outcome recorded between 56-212 days after cohort entry.

• Report overall mean (sd) of the primary outcome.

	Optum CDM
Outcome – Lab value HbA1cmean (sd)	7.24 (1.01)

8. Initial Power Assessment

Analysis report name:

For liraglutide vs. glimepiride

Optum CDM – see file LEAD-2_programming_steps and output of "STEP 2 - INITIAL POWER Assessment - PS matching on age, gender, CCI (with dummy outcome) - Paragraphs 8 of the protocol"

Date conducted: 06/16/2021

In order to complete the initial power analysis, the dummy outcome of a 90-day gap in database enrollment will be used. This outcome is used to ensure that no information on the comparative risks of the outcomes of interest are available at this stage.

Complete a 1:1 PS-matched comparative analysis using this outcome. PS should include only 3 covariates: age, gender and combined comorbidity index. Power calculations are based on the formulas from Julios et al. (2008).

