Number of patients			-			-
Age categories						

14.2 Table 2: Follow-up time

Patient Group	Median Follow-Up Time (Days) [IQR]
Overall Patient Population	
Referent	
Exposure	

14.3 Table 3: Censoring events

	Overall	Referent	Exposure
Outcome			
Death			
Start of an additional exposure			
End of index exposure			
Specified date reached			
End of patient data			
End of patient enrollment			

14.4 Table 4: Results from primary analyses;

Analysis	No. exposed events	No. referent events	Exposed rate	Referent rate	HR (95% CI)
Crude					
Analysis 1					
Analysis 2					

HR, Hazard Ratio; CI, Confidence Interval.

14.5 Table 5: Results from secondary analyses.

15. References

Julious SA. Sample sizes for clinical trials with Normal data. Statist. Med. 2004; 23:1921-1986. Sealed Envelope Ltd. 2012. Power calculator for continuous outcome non-inferiority trial. [Online] Available from: https://www.sealedenvelope.com/power/continuous-noninferior/ [Accessed Fri May 07, 2021].

#	LEAD-2 trial definitions	Implementation in routine care		for further details or any missing information: 618wrywYjEaXzfLTcuK-VCenb6b-gV?usp≕sharing
	Trial details - clini	ICD-10 codes are not listed in this document because of excel cell size limitations and excessive number of ICD-10 codes. Full ICD-10 code lists will be available in the above Google Drive Folder (link above). ICD-9 to ICD-10 code conversions were completed using a SAS macro that implements forward/backward mapping based on the CMS ICD-9 to ICD-10 mapping: https://www.nber.org/data/icd/9-icd-10-cm-and-nex-crosswalk-general-equivalence-mapping.html		
	EXPOSURI	E vs. COMPARISON	References/Rationale	Color coding

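### The only results shell for the primary analysis (Table 4) asks for events, rates and a hazard ratio, while the endpoint is a continuous HbA1c change judged against a 0.4 limit and no passage names the estimator

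*Combined protocol and SAP*

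**What the plan says.** **Endpoint and target.** Section 6.3.1 defines the primary outcome as "Changes in HbA1c from baseline to 26 weeks of treatment (end of follow-up"; Section 1.3 agrees. Section 1.6 gives the result to be replicated: "Treatment difference in HbA1c was 0.0% [95% CI: -0.2 to 0.2", for each liraglutide dose against glimepiride.

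**Decision rule.** Section 1.4 reports that the trial concluded non-inferiority if the "upper limit of the two-sided 95% CI for the treatment difference was < 0.4" percent. Sections 8 and 10 carry the 0.4 limit and a two-sided alpha of 0.05 into the replication's power tables, with an outcome SD of 1.01.

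**Analysis.** Section 6.3.2 makes the as-treated analysis the main one and says "Multiple imputation will be used to handle missing values in the primary analysis", with complete case as a sensitivity analysis. It names no effect measure, model or estimator. Section 13.1 is a heading with nothing under it.

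**Results shell.** Table 4 (Section 14.4) has columns for the number of events and the rate in each arm, then a hazard ratio with 95% CI, footnoted "HR, Hazard Ratio; CI, Confidence Interval". Its rows are crude and two numbered analyses that are not described. Tables 1 to 3 cover baseline, follow-up time and censoring. Table 5 is a bare heading for secondary analyses.

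**What counts as an HbA1c event.** Section 7 uses a binary flag for "presence or absence of an HbA1c result within 56-212 days after cohort entry". The outcome row of its censoring table is footnoted as "patients with outcome recorded between 56-212 days after cohort entry".

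**The concern.** A hazard ratio needs an event. The endpoint has none: every patient has an HbA1c change, observed or missing. The only thing the document counts as an outcome event is the appearance of a laboratory result, so Table 4 completed as printed would compare how soon and how often patients were tested. That is not glycaemic control, and a unitless ratio cannot be compared with a limit of 0.4 HbA1c percentage points or with the trial's 0.0 (-0.2 to 0.2).

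The mismatch matters beyond the header because nothing else in the document fills the gap. Section 7 deliberately keeps the HbA1c comparison blind: no measures of association will be computed, "nor will mean and standard deviation of the HbA1c outcome stratified by treatment group". Table 4 then has no place where those per-arm values would be reported. If the estimator is not written down before Section 13 is run, the choice between a raw and a baseline-adjusted difference could be made after outcomes are visible by arm.

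**Working it through.** **1. The plan's own sample size is a comparison of means.** Inputs from Sections 8 and 10: SD 1.01, limit 0.4, power 90%, true difference 0. Formula: n per group = 2 × SD² × (z_alpha + z_beta)² / limit².
- One-sided alpha 0.05: 2 × 1.0201 × (1.645 + 1.282)² / 0.16 = 109.2, so 110. This reproduces the stated figure.
- Two-sided 0.05, as labelled: 2 × 1.0201 × (1.960 + 1.282)² / 0.16 = 134.0, so 134. This does not match; 110 per group would give 83.6% power.

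No event count, rate or hazard enters the calculation. The matched 373 per group exceeds both figures, so there is no shortfall. The mismatch does show why the CI level of the decision rule should be stated for the replication.

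**2. What Table 4 would contain if filled literally.** From the Section 7 censoring table (unmatched), patients with a result recorded:
- Liraglutide: 233/378 = 61.6%
- Glimepiride: 2,029/3,092 = 65.6%
- Overall: 2,262/3,470 = 65.2%

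These are proportions tested. The rates and hazard ratio that Table 4 asks for need per-arm person-time, which is not given. Median follow-up is 88 and 101 days. Using the medians as a crude stand-in for person-time (assumption), the rate ratio is (0.616/88) / (0.656/101) = 1.08. Counting from day 56, where Section 6.3.2 starts follow-up, it is (0.616/32) / (0.656/45) = 1.32. The value cannot be pinned down, and in every form it concerns testing.

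**3. A mean difference can be set against 0.4.** With all 373 per arm observed, 95% half-width = 1.96 × SD × √(2/373):
- SD 1.01 (Section 10): 0.145
- SD 1.2 (the trial's planning value, Section 1.4): 0.172

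The 1.01 is the SD of the follow-up HbA1c level (mean 7.24), not of the change.

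**4. The unnamed estimator changes the interval.** Baseline SDs in Appendix B are 0.96 (n = 3,096) and 0.99 (n = 378), pooled 0.963. The baseline-to-follow-up correlation r is not given; 0.2 to 0.6 is assumed.
- Raw change: SD = √(0.963² + 1.01² − 2r × 0.963 × 1.01) = 1.25 to 0.88; half-width 0.179 to 0.127.
- Adjusted for baseline: SD = 1.01 × √(1 − r²) = 0.99 to 0.81; half-width 0.142 to 0.116.

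Both assume complete outcomes, so they illustrate the choice and do not forecast precision.

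**5. Why the rows need labels.** Applying the unmatched shares to the matched arms (assumption): 373 × 0.616 = 230 and 373 × 0.656 = 245 observed, so 746 − 475 = 271 (36%) missing. Using either arm's share for both gives 34% to 38%. With that much missing, the multiple-imputation and complete-case results must be distinguishable.

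**6. Table 3.** Section 7 reports a combined row for added antidiabetic drugs, nursing home admission and metformin discontinuation: 349/3,470 = 10.1%. The Section 14.3 shell has no such row. The overall column sums correctly: 2,262 + 2 + 8 + 368 + 336 + 37 + 108 + 349 = 3,470. The per-arm entries printed for this row (22 and 314) sum to 336 and repeat the maximum-follow-up row. By subtraction they would be 378 − 347 = 31 and 3,092 − 2,774 = 318, which sum to 349.

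**The case against.** The best defence is that Table 4 is a leftover template and nobody would read it literally. There is good support for this. Section 7 runs a report on the continuous HbA1c outcome, the power tables use an SD and a limit, and the reference list cites a calculator for continuous non-inferiority outcomes. The tables in Sections 7 and 9 show that shells are adapted when filled: they add a row and rename another compared with Table 3. Section 13.1 may be a field to complete later, and implementation detail sits in a programming file outside this document.

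Most of that stands, and it limits the point in four ways:
- A reader might infer that a survival analysis of HbA1c testing is planned. The documents do not support that; the intended mean difference can be inferred.
- A reader might take 61.6% / 65.6% = 0.94 as the crude Table 4 result. It is a ratio of proportions tested, not a rate ratio or hazard ratio, and the follow-up medians suggest a ratio above 1.
- A reader might say there is no decision rule. Section 1.4 states one, and Sections 8 and 10 carry its limit and alpha. What is missing is a sentence adopting it for the replication.
- A reader might say the estimator will be chosen after the arms are compared. The staged, blinded workflow supports only that it could be.

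What the defence does not supply is any passage naming the effect measure. Table 4 is the only one that does, and Section 12 directs that this document be uploaded at registration.

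**Conclusion.** The point holds and should be fixed before the Section 13 analyses are run. The one shell for the primary result specifies an effect measure that cannot answer the replication question, and no other text names the right one. Read literally, the plan yields a contrast in HbA1c testing that cannot be compared with 0.4. Read charitably, it yields a mean difference whose estimator and pooling are not stated.

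The contradiction itself rests on no assumption. The 36% missing and the half-widths do: they use unmatched shares and SDs, and an assumed correlation. They show only that row labels and the estimator matter. A reader might look for a power problem here, but the documents do not show one: 373 per arm exceeds both 110 and 134. The missing Table 3 row is minor.

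**What to change.** **Table 4.** Replace the columns with, per arm: number matched, number with an observed outcome, and mean (SD) of baseline, follow-up and change in HbA1c. Then give the mean difference (liraglutide minus glimepiride) with a two-sided 95% CI. Label the rows crude; matched with multiple imputation (primary); matched complete case (sensitivity).

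**Section 6.3.2 or 13.1.** Name the mean-difference estimator and say that it is pooled over imputations. Adjustment for baseline HbA1c is preferable, since it is already extracted (Appendix B). State that the replication adopts the Section 1.4 rule: non-inferior if the upper limit of the two-sided 95% CI is below 0.4%.

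**Table 3 (minor).** Add the combined censoring row used in Sections 7 and 9.

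**Cost.** Wording and table shells only; no new data or patients. The date in Section 12 is blank, so the document does not show whether it has been registered. If it has, a dated update before the comparative analyses is enough.

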15	Any contraindications to metformin or glimepiride (according to local requirements).	Diabetic ketoacidosis (DKA): ICD9 diagnosis: 250.1x ICD10 diagnosis: E10.1x, E11.1x, E13.1x, E08.1x, E09.1x	
		Other metabolic acidosis: ICD9 diagnosis: 276.2 ICD10 diagnosis: E87.2	
1		NB. All patients no treated with metformin at cohort entry have been excluded from the eligible cohort, assuming that all	
		Measured 1825 days prior to and including day of drug initiation in any diagnosis position and inpatient or outpatient care setting:	
16	Subjects with medical history of multiple endocrine neoplasia type 2 (MEN2) or familial medullary thyroid carcinoma (FMTC) if total thyroidectomy has not been performed or cannot be ensured (i.e. posterior capsule of the thyroid gland not removed). This exclusion criterion has been added only in	ICD-9 diagnosis: 258.02, 258.03 ICD-10 diagnosis: E31.22, E31.23	
	Germany according to Substantial Protocol Amendment No. 2-DE, see Section 9.8.1.	NB. Thyroid carcinoma is already excluded with exclusion criterion 9	
		1	

	PREGNANCY DEFINITION
1. Delivery Codes	
Procedure Codes	Description
CPT-4 codes	
1960	Anesthesia for vaginal delivery only
1961	Anesthesia for cesarean delivery only
1962	Anesthesia for urgent hysterectomy following delivery
1963	Anesthesia for cesarean hysterectomy w/o any labor analgesia/anesthesia care
1967	Neuraxial labor analgesia/anesthesia, planned vaginal delivery
1968	Anesthesia for cesarean delivery following neuraxial labor analgesia/anesthesia
1969	Anes for cesarean hysterectomy following neuraxial labor analgesia/anesthesia
59050	Fetal monitoring in labor, physician w/written report; s & i
59051	Fetal monitoring in labor, physician w/written report; intrepretation only
59400	ROUTINE TOTAL OBSTETRIC CARE including antepartum care, vaginal delivery (with or without episiotomy, and/or forceps) and postpartum care.
59409	Vaginal delivery only (w/wo episiotomy &/or forceps)
59410	Vaginal delivery only (w/wo episiotomy &/or forceps); w/postpartum care
59412	Ext cephalic version, w/wo tocolysis
59414	Delivery of placenta (separate proc)
59430	Postpartum care only
59510	Routine obstetric care w/antepartum care, cesarean delivery, & postpartum care
59514	Cesarean delivery only
59515	Cesarean delivery only; w/postpartum care
59525	Subtotal/total hysterectomy after cesarean delivery
59610	Routine obstetric care including antepartum care, vaginal delivery (with or without episiotomy, and/or forceps) and postpartum care, after previous cesarean delivery
59612	Vaginal delivery only, after previous cesarean delivery (with or without episiotomy and/or forceps)
59614	Vaginal delivery only, previous cesarean delivery w/postpartum care
59618	Routine obstetric care including antepartum care, cesarean delivery, and postpartum care, following attempted vaginal delivery after previous cesarean delivery
59620	Cesarean delivery after failed vaginal delivery, previous cesarean delivery
59622	Cesarean delivery after failed vaginal delivery, previous cesarean delivery; w/postpartum care
99436	Attendance at delivery, at request of delivering physician, & stabilization of newborn
99440	Newborn resuscitation
ICD-9 procedure codes	
72.xx	Forceps, vacuum, & breech
73.xx	Other including manual delivery
74xx	Cesarean section
75.4x	Manual removal of placenta
ICD-10 procedure codes	
Normal Delivery	
10E0XZZ	Delivery of Products of Conception, External Approach
C-Section	
10D00Z0	Extraction of Products of Conception, High, Open Approach
10D00Z1	Extraction of Products of Conception, Low, Open Approach
10D00Z2	Extraction of Products of Conception, Extraperitoneal, Open Approach
Other assisted delivery (fo	rceps, vacuum, internal version, other)
10D07Z3	Extraction of Products of Conception, Low Forceps, Via Natural or Artificial Opening
10D07Z4	Extraction of Products of Conception, Mid Forceps, Via Natural or Artificial Opening
10D07Z5	Extraction of Products of Conception, High Forceps, Via Natural or Artificial Opening
10D07Z6	Extraction of Products of Conception, Vacuum, Via Natural or Artificial Opening
10D07Z7	Extraction of Products of Conception, Internal Version, Via Natural or Artificial Opening
10D07Z8	Extraction of Products of Conception, Other, Via Natural or Artificial Opening

2. Identify preterm births Codes that have a specific gestational age mentioned Definition ICD-9 code 765.21 Less than 24 completed weeks of gestation 765.22 24 completed weeks of gestation 765.23 25-26 completed weeks of gestation 765.24 27-28 completed weeks of gestation 765.25 29-30 completed weeks of gestation 765.26 31-32 completed weeks of gestation 765.27 33-34 completed weeks of gestation 765.28 35-36 completed weeks of gestation ICD-10 code Definition P07.21 Extreme immaturity of newborn, gestational age less than 23 completed weeks P07.22 Extreme immaturity of newborn, gestational age 23 completed weeks P07.23 Extreme immaturity of newborn, gestational age 24 completed weeks P07.24 Extreme immaturity of newborn, gestational age 25 completed weeks P07.25 Extreme immaturity of newborn, gestational age 26 completed weeks P07.26 Extreme immaturity of newborn, gestational age 27 completed weeks P07.31 Preterm newborn, gestational age 28 completed weeks P07.32 Preterm newborn, gestational age 29 completed weeks P07.33 Preterm newborn, gestational age 30 completed weeks P07.34 Preterm newborn, gestational age 31 completed weeks P07.35 Preterm newborn, gestational age 32 completed weeks P07.36 Preterm newborn, gestational age 33 completed weeks P07.37 Preterm newborn, gestational age 34 completed weeks P07.38 Preterm newborn, gestational age 35 completed weeks P07.39 Preterm newborn, gestational age 36 completed weeks b. Codes indicating extreme prematurity ICD-9 code Definition 765 Disorders relating to extreme immaturity of infant 765.00 Extreme immaturity, unspecified [weight] 765.01 Extreme immaturity, less than 500 grams 765.02 Extreme immaturity, 500-749 grams 765.03 Extreme immaturity, 750-999 grams 765.04 Extreme immaturity, 1,000-1,249 grams 765.05 Extreme immaturity, 1,250-1,499 grams 765.06 Extreme immaturity, 1,500-1,749 grams 765.07 Extreme immaturity, 1,750-1,999 grams 765.08 Extreme immaturity, 2,000-2,499 grams ICD-10 code Definition P07.2 Extreme immaturity of newborn P07.20 Extreme immaturity of newborn, unspecified weeks of gestation 042.012 Preterm premature rupture of membranes, onset of labor within 24 hours of rupture, second trimester c. Other preterm codes Definition ICD-9 code 765.1 Disorders relating to other preterm infants 765.10 Other preterm infants, unspecified [weight] Other preterm infants, less than 500 grams 765.11 765.12 Other preterm infants, 500-749 grams 765.13 Other preterm infants, 750-999 grams

765.14	Other preterm infants, 1,000-1,249 grams
765.15	Other preterm infants, 1,250-1,499 grams
765.16	
	Other preterm infants, 1,500-1,749 grams
765.17	Other preterm infants, 1,750-1,999 grams
765.18	Other preterm infants, 2,000-2,499 grams
644.21	Onset of delivery before 37 completed weeks of gestation
ICD-10 code	Definition 500 hours of the state of the sta
P05.01	Disorders of newborn related to slow fetal growth and fetal malnutrition less than 500 grams
P05.02	Disorders of newborn related to slow fetal growth and fetal malnutrition, 500-749 grams
P05.03	Disorders of newborn related to slow fetal growth and fetal malnutrition, 750-999 grams
P05.04	Disorders of newborn related to slow fetal growth and fetal malnutrition, 1000-1249 grams
P05.05	Disorders of newborn related to slow fetal growth and fetal malnutrition, 1250-1499 grams
P05.06	Disorders of newborn related to slow fetal growth and fetal malnutrition, 1500-1749 grams
P05.11	Newborn small for gestational age, less than 500 grams
P05.12	Newborn small for gestational age, 500-749 grams
P05.13	Newborn small for gestational age, 750-999 grams
P05.14	Newborn small for gestational age, 1000-1249 grams
P05.15	Newborn small for gestational age, 1250-1499 grams
P05.16	Newborn small for gestational age, 1500-1749 grams
P07.01	Extremely low birth weight newborn, less than 500 grams
P07.02	Extremely low birth weight newborn, 500-749 grams
P07.03	Extremely low birth weight newborn, 750-999 grams
P07.14	Other low birth weight newborn,1000-1249 grams
P07.15	Other low birth weight newborn,1250-1499 grams
P07.16	Other low birth weight newborn, 1500-1749 grams
P07.3	Preterm [premature] newborn [other]
P07.30	Preterm newborn, unspecified weeks of gestation
060.1	Preterm labor with preterm delivery
042.01	Preterm premature rupture of membranes, onset of labor within 24 hours of rupture
042.019	Preterm premature rupture of membranes, onset of labor within 24 hours of rupture, unspecified trimester
042.013	Preterm premature rupture of membranes, onset of labor within 24 hours of rupture, third trimester
Other Codes	Description
ICD-9	
644.2	early onset of delivery
644.2	Early onset of delivery, unspecified as to episode of care or not applicable
644.21	Early onset of delivery, delivered, with or without mention of antepartum condition
776.6	anemia of prematurity
362.2	retinopathy of prematurity, unspecified
362.22	retinopathy of prematurity, stage 0
362.23	retinopathy of prematurity, stage 1
362.24	retinopathy of prematurity, stage 2
362.25	retinopathy of prematurity, stage 3
362.26	retinopathy of prematurity, stage 4
362.27	retinopathy of prematurity, stage 5
CPT	Technopathy or prematerity, stage of
49491	repair, initial inguinal hernia, preterm infant (younger than 37 weeks gestation at birth), performed from birth up to 50 weeks postconception
49492	repair, initial inguinal hernia, preterm infant (younger than 37 weeks gestation at birth), performed from birth up to 50 weeks postconception
67229	treatment of extensive or progressive retinopathy, 1 or more sessions; preterm infant (less than 37 weeks gestation at birth), performed from
836	anesthesia for hernia repairs in the lower abdomen not otherwise specified, infants younger than 37 weeks gestational age at birth
ICD-10 code	Definition

H35.1	Retinopathy of prematurity
P61.2	Anemia of prematurity
	V for ICD-9 and Z for ICD-10 codes excluded)
ICD9 Code	Description
V27.2	Twins both liveborn
V27.3	Mother with twins one liveborn and one stillborn
V27.4	Mother with twins both stillborn
V27.5	Other multiple birth, all liveborn
V27.6	Other multiple birth, some liveborn
V31	Twin, mate liveborn
V32	Twin birth mate stillborn
V33	Twin, unspecified
V34	Other multiple, mates all liveborn
V35	Other multiple birth (three or more) mates all stillborn
V36	Other multiple, mates live- and stillborn
V37	Other multiple, unspecified
651	Multiple gestation
651.0x	Twin Pregnancy
651.1x	Triplet pregnancy
651.2x	Quadruplet pregnancy
651.3x	Twin pregnancy with fetal loss and retention of one fetus
651.4x	Triplet pregnancy with fetal loss and retention of one or more fetus(es)
651.5x	Quadruplet pregnancy with fetal loss and retention of one or more fetus(es)
651.6x	Other multiple pregnancy with fetal loss and retention of one or more fetus(es)
651.7x	Multiple gestation following (elective) fetal reduction
651.8x	Other specified multiple gestation
651.9x	Unspecified multiple gestation
652.6x	Multiple gestation with malpresentation of one fetus or more
660.5x	Locked Twins
662.3x	Delayed delivery of second twin, triplet, etc.
761.5x	Multiple pregnancy
ICD10 Code	Description
O30xxxx	Multiple gestation
O31xxxx	Complications specific to multiple gestation
043.02	Fetus-to-fetus placental transfusion syndrome
063.2	Delayed delivery of second twin, triplet, etc.
Z37.2	Twins, both liveborn
Z37.3	Twins, one liveborn and one stillborn
Z37.5	Other multiple births, all liveborn
Z37.50	Multiple births, unspecified, all liveborn
Z37.51	Triplets, all liveborn
Z37.52	Quadruplets, all liveborn
Z37.53	Quintuplets, all liveborn
Z37.54	Sextuplets, all liveborn
Z37.59	Other multiple births, all liveborn
Z37.6	Other multiple births, some liveborn
Z37.60	Multiple births, unspecified, some liveborn
Z37.61	Triplets, some liveborn
Z37.62	Quadruplets, some liveborn
Z37.63	Quintuplets, some liveborn

Z37.64	Sextuplets, some liveborn
Z37.69	Other multiple births, some liveborn
Z38.3	Twin liveborn infant, born in hospital
Z38.30	Twin liveborn infant, delivered vaginally
Z38.31	Twin liveborn infant, delivered by cesarean
Z38.4	Twin liveborn infant, born outside hospital
Z38.5	Twin liveborn infant, unspecified as to place of birth
Z38.6	Other multiple liveborn infant, born in hospital
Z38.61	Triplet liveborn infant, delivered vaginally
Z38.62	Triplet liveborn infant, delivered by cesarean
Z38.63	Quadruplet liveborn infant, delivered vaginally
Z38.64	Quadruplet liveborn infant, delivered by cesarean
Z38.65	Quintuplet liveborn infant, delivered vaginally
Z38.66	Quintuplet liveborn infant, delivered by cesarean
Z38.68	Other multiple liveborn infant, delivered vaginally
Z38.69	Other multiple liveborn infant, delivered by cesarean
Z38.7	Other multiple liveborn infant, born outside hospital
Z38.8	Other multiple liveborn infant, unspecified as to place of birth
P01.5	Newborn affected by multiple pregnancy
3. Post-Term Code	25
ICD-9 code	Definition
645	Late Pregnancy
645.1	Post term pregnancy
645.1	Post term pregnancy, unspecified as to episode of care or not applicable
645.11	Post term pregnancy, delivered, with or without mention of antepartum condition
645.13	Post term pregnancy, antepartum condition or complication
645.2	Prolonged pregnancy
645.2	Prolonged pregnancy, unspecified as to episode of care or not applicable
645.21	Prolonged pregnancy, delivered, with or without mention of antepartum condition
645.23	Prolonged pregnancy, antepartum condition or complication
766.2	Late infant, not 'heavy-for-dates'
766.21	Post-term infant
766.22	Prolonged gestation of infant

ICD-10 code Definition
O48 Late pregnancy
O48.0 Post-term pregnancy
O48.1 Prolonged pregnancy

P08.2 Late newborn, not heavy for gestational age

P08.21 Post-term newborn

P08.22 Prolonged gestation of newborn Z3A.41 41 weeks gestation of pregnancy Z3A.42 42 weeks gestation of pregnancy

Z3A.49 Greater than 42 weeks gestation of pregnancy

4. Codes indicating a prenatal care visit:

ICD-9: V220x, V221x, V23xx

Anti-diabetic treatments (other than insulin)

1st and 2nd Generation Sus (excluding glimepiride)

GLIPIZIDE/METFORMIN HCL

ACETOHEXAMIDE

GLYBURIDE, MICRONIZED

TOLBUTAMIDE

GLYBURIDE/METFORMIN HCL

TOLAZAMIDE

CHLORPROPAMIDE

GLYBURIDE

GLIPIZIDE

AGIs

ACARBOSE

MIGLITOL

DPP-4 Inhibitors

ALOGLIPTIN BENZOATE

DAPAGLIFLOZIN PROPANEDIOL/SAXAGLIPTIN HCL

ERTUGLIFLOZIN PIDOLATE/SITAGLIPTIN PHOSPHATE

SAXAGLIPTIN HCL/METFORMIN HCL

LINAGLIPTIN

ALOGLIPTIN BENZOATE/METFORMIN HCL

ALOGLIPTIN BENZOATE/PIOGLITAZONE HCL

EMPAGLIFLOZIN/LINAGLIPTIN

SAXAGLIPTIN HCL

SITAGLIPTIN PHOSPHATE/METFORMIN HCL

SITAGLIPTIN PHOSPHATE/SIMVASTATIN

SITAGLIPTIN PHOSPHATE

Glitazones

ALOGLIPTIN BENZOATE/PIOGLITAZONE HCL

PIOGLITAZONE HCL

PIOGLITAZONE HCL/GLIMEPIRIDE

PIOGLITAZONE HCL/METFORMIN HCL

ROSIGLITAZONE MALEATE

ROSIGLITAZONE MALEATE/GLIMEPIRIDE

ROSIGLITAZONE MALEATE/METFORMIN HCL

GLP-1 RA (excluding liraglutide monotherapy)

ALBIGLUTIDE

DULAGLUTIDE

EXENATIDE

EXENATIDE MICROSPHERES

INSULIN DEGLUDEC/LIRAGLUTIDE

INSULIN GLARGINE, HUMAN RECOMBINANT ANALOG/LIXISENATIDE

LIXISENATIDE

SEMAGLUTIDE

Meglitinides

NATEGLINIDE

REPAGLINIDE

REPAGLINIDE/METFORMIN HCL

SGLT-2 Inhibitors

CANAGLIFLOZIN

CANAGLIFLOZIN/METFORMIN HCL

DAPAGLIFLOZIN PROPANEDIOL/SAXAGLIPTIN HCL

ERTUGLIFLOZIN PIDOLATE

ERTUGLIFLOZIN PIDOLATE/SITAGLIPTIN PHOSPHATE

DAPAGLIFLOZIN PROPANEDIOL/METFORMIN HCL

EMPAGLIFLOZIN/LINAGLIPTIN

EMPAGLIFLOZIN

DAPAGLIFLOZIN PROPANEDIOL

ERTUGLIFLOZIN PIDOLATE/METFORMIN HCL

EMPAGLIFLOZIN/METFORMIN HCL

Insulin

Bolus insulins

INSULIN GLULISINE

INSULIN REGULAR, BEEF-PORK

INSULIN ASPART (NIACINAMIDE)

INSULIN REGULAR, HUMAN/INSULIN RELEASE UNIT

INSULIN REGULAR, HUMAN BUFFERED

INSULIN REGULAR, HUMAN/INSULIN RELEASE UNIT/CHAMBER/INHALER

INSULIN ASPART

INSULIN ASPART PROTAMINE HUMAN/INSULIN ASPART

INSULIN LISPRO PROTAMINE AND INSULIN LISPRO

INSULIN LISPRO

INSULIN REGULAR, HUMAN

Intermediate and Long-acting Insulins

INSULIN DEGLUDEC

INSULIN DETEMIR

INSULIN DEGLUDEC/LIRAGLUTIDE

INSULIN NPH HUMAN AND INSULIN REGULAR HUMAN SEMI-SYNTHETIC

INSULIN NPH HUMAN SEMI-SYNTHETIC

INSULIN ISOPHANE NPH, BF-PK

[figure not shown]
INSULIN GLARGINE, HUMAN RECOMBINANT ANALOG/LIXISENATIDE

INSULIN GLARGINE, HUMAN RECOMBINANT ANALOG

INSULIN NPH HUMAN ISOPHANE

INSULIN NPH HUMAN ISOPHANE/INSULIN REGULAR, HUMAN

